21. History of autonomic dysfunction, including amyloidosis, Parkinson's disease, autoimmune disease, spinal cord injury

G. STATISTICAL CONSIDERATIONS:

464 The primary outcome is the difference in glycemic control (as measured by HbA1c) at 6 and 12
465 months between the vagus nerve cryoablation group and the lifestyle intervention group.
466 Summary statistics including mean, median, and standard deviations for the changes in HbA1c
467 at 3, 6, 9 and 12 months will be computed. We will then compare the changes at 6 months
468 between the two treatment groups by a nonparametric Wilcoxon test or a two-sample t-tests
469 (with appropriate data transformation if needed). We will conduct one-way ANOVA to estimate
470 the mean difference in glycemic parameters at 6 and 12 months month between the two
471 treatment groups. We may further adjust for some important confounders by using linear
472 regression models. We will also assess the glycemic control outcomes simultaneously across
473 different follow-up visits (i.e. 12, 24 weeks) through repeated measures ANOVA models, which
474 appropriately account for within-subject correlations in the measurements. In addition, we will
475 consider repeated measures linear regression model with visits incorporated as a continuous time
476 variable. We may include other covariates in the model when feasible.

477 The primary safety endpoint of the trial is the occurrence of death and all procedure related
478 complications, such as bleeding, infection, pneumothorax, hemothorax, pulmonary injury,
479 complications of sedation, pain requiring hospital admission or treatment, dysphagia,
480 gastroparesis, nausea and vomiting, and gastrointestinal ulceration for the duration of the study.
481 We will first use the Chi-square test (or Fisher's exact test) to compare the occurrence of this
482 primary safety endpoint between the two treatment groups. We will perform logistic regression
483 to evaluate the group difference while adjusting for other potential confounders such as age,
484 gender, and BMI. In addition, we will compare the number of procedure related complications
485 by using Poisson regression or Negative Binomial regression between the two treatment groups.
486 Standard model selection (e.g. forward, backward variable selection) and model checking
487 procedures (e.g. deviance residual plot and Hosmer- Lemeshow test) will be performed to ensure
488 the adequacy of the final models.

489

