490 Secondary outcomes will be compared between the two treatment groups. For continuous
491 secondary outcomes, we will follow the plan proposed for primary outcome. For discrete
492 secondary outcomes, we will first conduct cross-sectional comparisons based on Chi-squared
493 tests or Fisher's exact test. If the discrete outcome is measured at multiple visits, we will fit
494 repeated measures generalized linear models to simultaneously assess the difference in the
495 longitudinal discrete outcome between the two treatment groups. Other covariates may be
496 included in the models if feasible.

497

498 **Sample Size Calculation and Power Analysis:**

499 This study is generating pilot data for utilization of this procedure in a novel patient population.
500 Given the 15 patients per group, taking into account 20% attrition rate, we would have 12
501 patients per group. In this case, we would have 80% power to detect a difference in glycemic
502 control outcome change that equals 1.2 times the standard deviation of the glycemic control
503 outcome change. The data generated from this study will provide useful relevant preliminary
504 data for planning larger randomized studies.

505

506

507

IV. DATA HANDLING AND RECORD KEEPING:

508 Data collection records with personal identifiers will be stored in locked file cabinets. Blood
509 samples drawn in conjunction with this study will not be labeled with information that could
510 directly identify study subjects. De-identified serum samples will be stored. We may use the
511 samples collected and stored in this study for future studies without a separate IRB consent for
512 the subjects. This will be explained to the study subjects at the time of consent. If we use the
513 samples in future studies, coded identifiers will be used. The informed consent will make it clear
514 that subjects can request their samples to be destroyed at any time. Presentation of the study
515 results at regional or scientific meetings or in publications will not identify subjects. Access to
516 research and confidential records will be limited to clinical investigators, research coordinators,
517 and the IRB at Emory University.
518

519 Study coordinators and/or investigators will collect baseline and follow up data, complete the
520 CRF (case report form) and enter data into RedCap (electronic database provided by the Emory
521 Research Information Technology Department). Baseline data will include demographics

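### The 6-month HbA1c comparison leaves the choice of test and any covariate open; one prespecified model adjusted for baseline HbA1c would be a cheap improvement, though not mainly for power

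*Combined protocol and SAP*

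**What the plan says.** Section III.G opens: "The primary outcome is the difference in glycemic control (as measured by HbA1c) at 6 and 12" months. It then plans descriptive summaries and the formal comparison: "at 3, 6, 9 and 12 months will be computed. We will then compare the changes at 6 months", made "between the two treatment groups by a nonparametric Wilcoxon test or a two-sample t-tests". Transformation is allowed if needed, without a criterion. No rule says which test is used.

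A one-way ANOVA at 6 and 12 months follows. With two groups this is the same unadjusted comparison as the t-test.

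Adjustment is optional in both places where it appears for HbA1c: "treatment groups. We may further adjust for some important confounders by using linear" regression and, for the repeated-measures regression, "variable. We may include other covariates in the model when feasible". Neither sentence names a covariate. The only covariates named in III.G are age, gender and BMI, and they belong to the logistic model for the safety endpoint ("to evaluate the group difference while adjusting for other potential confounders such as age").

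The same plan covers the continuous secondary outcomes: "secondary outcomes, we will follow the plan proposed for primary outcome".

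Baseline HbA1c is available for everyone. It is an entry criterion (7.5-10.5%, section III.F) and is marked at baseline in the laboratory table of section III.C.

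**The concern.** A change score uses the baseline value but fixes its coefficient: it assumes that the 6-month value moves one for one with baseline. If the true slope differs from 1, a chance difference in baseline HbA1c between arms carries over into the estimated treatment effect. In a trial this small such differences are common, and the recruitment and randomization section describes only a computer-generated table, with no stratification on HbA1c.

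The trial is also unblinded. If the test and covariates are settled after the data are in, they could be settled with results by arm in view, and the nominal error rate would no longer be guaranteed. The sample size section says that the data are meant to inform larger randomized trials. One estimate fixed in advance serves that better than several unranked candidates.

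**Working it through.** **Inputs from the documents.** 15 randomized per arm and 20% attrition, so 15 x 0.8 = 12 per arm; target difference 1.2 SD of the change; power 80% (sample size section).

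**Assumed, because the documents do not give them.** Two-sided alpha of 0.05; correlation rho between baseline and 6-month HbA1c from 0.3 to 0.9; ratio k of baseline SD to follow-up SD of 1, 0.85 or 0.7; normal data.

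**1. The plan's own figure.** Two-sample t-test on change: noncentrality 1.2 x sqrt(12/2) = 2.94 on 22 df gives 80.2% power. The stated 80% reproduces. The Wilcoxon alternative gives about 76% by simulation with normal data.

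**2. Power of the baseline-adjusted model.** The residual variance relative to the change-score variance is

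(1 - rho^2) / (1 + k^2 - 2 rho k).

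The test has 21 df, and chance imbalance in the covariate costs on average a variance factor of about 1 + 1/(24 - 4) = 1.05.

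- Best cell, k = 1 and rho = 0.3: ratio 0.91/1.40 = 0.65. Effective difference 1.2/sqrt(0.65 x 1.05) = 1.45, power 92%.
- Worst cell, k = 0.7 and rho = 0.7: ratio 0.51/0.51 = 1. Effective difference 1.2/sqrt(1.05) = 1.17, power 78%.

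Full grid, 12 per arm, averaged over random imbalance, to be read against 80.2%:

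| k | rho 0.3 | 0.5 | 0.7 | 0.8 | 0.9 |
|---|---|---|---|---|---|
| 1 | 92.3% | 88.4% | 84.3% | 82.2% | 80.2% |
| 0.85 | 88.4% | 83.9% | 79.9% | 78.4% | 78.7% |
| 0.7 | 84.3% | 80.2% | 78.1% | 79.2% | 85.3% |

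The 7.5-10.5% entry window limits the spread of baseline HbA1c, which favours the rows with k below 1. In those two rows, 6 of 10 cells show no gain: one equals the t-test and five fall below it, by about 2 points at worst. Simulation in three cells (20,000 runs each) agreed: 92.3%, 84.2% and 78.3% for (k, rho) = (1, 0.3), (0.85, 0.5) and (0.7, 0.7).

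**3. Chance imbalance.** The standard error of the baseline difference, in baseline SDs, is sqrt(2/12) = 0.408. The probability that it exceeds 0.5 in either direction is P(|Z| > 0.5/0.408) = 22%. With all 15 per arm, the standard error is 0.365 and the probability 17%.

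**4. Effect of such an imbalance on the unadjusted estimate.** In SDs of change, a 0.5 SD imbalance shifts it by

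0.5 x |rho - k| / sqrt(1 + k^2 - 2 rho k).

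This is 0 where rho = k, and 0.35/sqrt(1.40) = 0.30 at k = 1, rho = 0.3. If entry HbA1c were spread evenly over the window (assumed), its SD would be 3/sqrt(12) = 0.87 points, and the shift would be |slope - 1| x 0.433, or 0 to 0.30 HbA1c points.

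**5. Leaving the choice open.** Null simulations (40,000 runs per cell, 15 cells), reporting an effect whenever any candidate analysis is significant:

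- t-test or Wilcoxon: 5.5% to 5.9%.
- t-test with or without baseline adjustment: 5.6% to 7.9%.
- All three: 6.3% to 8.5%.

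Each analysis taken alone stays near or just below 5% (4.4% to 5.2%).

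**The case against.** The strongest reply is that nothing here is wrong. The t-test on change is valid, its power claim holds, and chance imbalance is ordinary sampling variation that its standard error already reflects. All of that stands. A reader might infer that the planned comparison is biased or its p-value invalid; the documents do not support that. What remains is that, given an observed imbalance, the unadjusted estimate is shifted in a known direction. Adjustment corrects this only on average, under a linear model with its slope estimated from about 24 patients.

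A reader might also infer that adjustment would lift power towards 92%. That needs equal SDs and a correlation of 0.3, neither of which the documents give, and the entry window points towards the rows where most cells show no gain.

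It is tempting to widen the type I calculation with models that add age, gender and BMI. Section III.G names these only for the safety model, so a figure built on them would not describe the HbA1c plan. The rates in step 5 are themselves worst cases, and for the two tests actually named the excess is under 1 point.

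The repeated-measures ANOVA covers "different follow-up visits (i.e. 12, 24 weeks) through repeated measures ANOVA models, which" omits later visits. That might be read as a gap, but 12 months has its own ANOVA, and section III.C describes the 9- and 12-month visits as safety follow-up after lifestyle counselling has ended. Restricting the model is a defensible choice.

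The plan does allow regression adjustment, and baseline HbA1c is an obvious candidate; but it is not named and the step is optional. Pilot status lowers the stakes. It does not remove the point, because the protocol plans formal tests and makes a power claim for this comparison. Finally, fixing the model does not settle which endpoint and visit are primary, which sections III.B, III.C and III.G describe differently.

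**Conclusion.** This is a real but small gap in prespecification: no rule selects the test, and no covariate is named for HbA1c. The case for change rests on having one fixed estimate and on protection against chance imbalance (above 0.5 SD in about 22% of trials with 12 per arm, worth 0 to 0.30 SD of change), with the avoidable worst-case type I error of about 6% to 8.5% second. Power is not a reason in itself: 78% to 92% adjusted against 80.2% unadjusted. Every figure except the reproduced power and the imbalance probability depends on the assumed correlation and SD ratio; all assume normal data, and those involving a test assume two-sided 0.05. The change is worth considering because it costs almost nothing.

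**What to change.** In section III.G, name one primary analysis: a linear model of HbA1c change from baseline to 6 months on treatment group and baseline HbA1c. Make a rank-based version (ranked change on treatment and ranked baseline) the sensitivity analysis for non-normal data, in place of an open choice between tests. Label models with any other covariates exploratory. For continuous secondary outcomes, adjust each for its own baseline value.

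The cost is SAP wording, with no new data or visits. The model uses one more degree of freedom and loses about 2 points of power at worst, when the slope of follow-up on baseline is near 1.

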216 guided cryoablation of the vagus nerve plus lifestyle intervention or lifestyle intervention alone.

217 **Group 1:** CT guided cryoablation of the vagus nerve plus lifestyle intervention (n=15).

218 **Group 2:** Lifestyle intervention by trained RD/CDE (n=15).

219 All subjects will have the procedure performed at Grady Memorial Hospital or Emory University
220 Hospital Midtown or Johns Creek by trained study personnel.
221

222 The study schema is shown below. Both groups will undergo screening for eligibility followed
223 by randomization. If the subject is not fasting at time of initial consent and screening, he/she will
224 be brought back for a subsequent visit with fasting blood work. Subjects must be randomized
225 within 4 weeks of the screening visit. If the randomization visit falls outside of the 4 week time
226 frame, the subject must undergo repeat screening procedures. In- person lifestyle counseling will
227 be provided at baseline visit for both groups. Those undergoing cryoablation will receive a phone
228 call 24 hour post-procedure to evaluate for any immediate complications, 1 week in person
229 follow up visit, as well as a safety call at 2 months. Subjects in both groups will have weekly
230 contact with RD and in person follow up visits at 4 weeks, 3 months, and 6 months. Blood work,
231 anthropometric data and questionnaires will be administered at baseline, 3 months, and 6 months.
232 Safety follow up appointments will be scheduled at 9 months and 12 months, though no further
233 lifestyle counseling will be provided after 6 months. Questioning regarding adverse events and
234 side effects will occur at all visits, as well as assessment of glycemic control. Anti-
235 hyperglycemic medications will be adjusted at visits under the direction of the endocrinologist,
236 or as needed for clinically significant hypo- or hyperglycemic events.

237
238

239 Blood work will be as follows: For all lab parameters, subject results must be within the
240 reference range unless otherwise specified by inclusion/exclusion criteria or if assessed by study
241 physician to be not clinically significant.

Lab test	Baseline	3 months	6 months	9 months	12 months
Complete metabolic panel	X	X	X	X	X
Pregnancy test	X	X	X	X	
HbA1c	X	X	X	X	X
Lipid panel	X		X		
Insulin level	X	X	X		X
TSH	X				

242
243

D. STUDY PROCEDURE:

244 **Cryoablation procedure (to be performed by [name] or [name]):** Subjects will

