301 any adjacent tissue or structures. Percutaneous CT-guided cryoneurolysis is well established and
302 routinely performed clinically. Specifically, [name] group has conducted three other
303 independent studies of peripheral nerve cryoablation, with procedural methods and outcome
304 measures that parallel the methods described herein⁵¹⁻⁵³. **Perhaps more importantly though,**
305 **the device is routinely used in clinical practice for the ablation of nerves as part of**
306 **percutaneous procedures that are very similar to the percutaneous cryovagotomy proposed**
307 **for this study**, including cryoablation for treatment of trigeminal neuralgia in the setting of
308 cancer⁵⁴, celiac plexus cryoablation,⁵⁵ as well as obturator nerve cryoablation, genitofemoral
309 nerve cryoablation, cryoablation of medial branch nerves in the setting of facetogenic lumbar
310 spine pain, and cryoablation of the inferior alveolar nerve.
311

312 Regarding the mechanism of cryoneurolysis, the premise upon which nerve cryoablation
313 procedures have been founded is the induction of a specific, reversible nerve injury.⁵⁶⁻⁵⁸ Nerve
314 injury classifications are classically described and correlated with clinical course following
315 trauma (crush, stretch, laceration, etc.), the most widely cited of which are the Seddon and
316 Sunderland classifications.^{59,60} it has been shown that temperatures induced by cryoablation
317 devices correspond with Sunderland 2 injuries in peripheral nerves.^{56,57} This precise neural injury
318 results in several well described events that lead to favorable clinical outcomes – cessation of
319 conduction, induced Wallerian degeneration, and *predictable regeneration* of axons upon an
320 intact connective tissue scaffold.^{57,58,61} the translation of these events (beyond conduction
321 cessation) has been documented as nerve function recovery in animal studies and in humans⁶²⁻⁶⁵.
322 62-66

323 Please see below with more details on the identified potential risks of procedures performed
324 percutaneously in interventional radiology:

325 1. *Bleeding*: The risk of bleeding is estimated to be <2%, and is specifically localized to
326 the site of the skin incision (4-5 mm). The risk of any internal bleeding is negligible since
327 it is a CT guided procedure and direct visualization of the probe during the procedure
328 limits any inadvertent involvement of vascular structures. After the procedure, patients

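### The repeated measures ANOVA for HbA1c stops at 24 weeks although 12 months is a named primary time, and the optional continuous-time model would misstate the effect at each visit if it is fitted as a straight line and the effect is not linear in time

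*Combined protocol and SAP*

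**What the plan says.** III.G Statistical Considerations opens with the outcome: "The primary outcome is the difference in glycemic control (as measured by HbA1c) at 6 and 12" months. It then sets out five pieces of analysis for HbA1c.

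- Summary statistics for the change, followed by the main test: "at 3, 6, 9 and 12 months will be computed. We will then compare the changes at 6 months", by Wilcoxon or t-test.
- A one-way ANOVA to estimate "the mean difference in glycemic parameters at 6 and 12 months month between the two" groups.
- Possible covariate adjustment by linear regression.
- A joint analysis across "different follow-up visits (i.e. 12, 24 weeks) through repeated measures ANOVA models, which" are there to account for within-subject correlation.
- An optional further model. The team will "consider repeated measures linear regression model with visits incorporated as a continuous time" variable. No non-linear term, set of visits, handling of baseline or group-by-time term is given.

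III.C Study Design has a laboratory table with HbA1c at baseline, 3, 6, 9 and 12 months. The text above it says: "Safety follow up appointments will be scheduled at 9 months and 12 months, though no further" counselling is given after 6 months. This applies to both groups.

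III.E Potential Risks and Benefits describes the mechanism. The premise on which nerve cryoablation "procedures have been founded is the induction of a specific, reversible nerve injury", and among the events that follow it lists cessation of "conduction, induced Wallerian degeneration, and *predictable regeneration* of axons upon an" intact scaffold. It gives no time to recovery and draws no consequence for HbA1c.

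**The concern.** The repeated measures ANOVA is the only longitudinal HbA1c analysis the plan commits to, and the one it relies on to handle correlation between visits. Its visit list is introduced by an expression that defines rather than illustrates, so as written it covers roughly months 3 and 6 only. It cannot say anything about 12 months, which III.A (Objective 1), III.B and III.G all name as a time for glycaemic control. It also makes no use of the scheduled 9- and 12-month values.

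The optional model could reach 12 months, but its time term is open. The plain default is a straight line, which assumes that the group difference keeps changing at a constant rate. After a single procedure whose mechanism is described as reversible, a plateau or a waning effect is at least as plausible. That is an inference from the mechanism, not something the protocol states.

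The sample size section says the data are meant to help plan larger trials. The size of the effect at 6 months and how much of it remains at 12 months are the quantities such planning would use.

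**Working it through.** **1. The plan's own figure.** The plan gives no number for the longitudinal models. Its one relevant figure is 80% power for a difference of 1.2 SD with 12 per group (15 × 0.8 = 12). With a two-sample t-test and two-sided alpha of 0.05 (assumed; the plan states none), the noncentrality is 1.2 × √(12/2) = 2.94 on 22 degrees of freedom, and power is 80.2%. The figure reproduces. It concerns a comparison at one visit, so nothing below affects it.

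**2. Visits needed against visits modelled.**

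| Month | HbA1c drawn | Named primary time in III.G | In the repeated measures ANOVA |
|---|---|---|---|
| 3 | yes | no | yes (12 weeks) |
| 6 | yes | yes | yes (24 weeks) |
| 9 | yes | no | no |
| 12 | yes | yes | no |

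This part needs no assumption about the effect.

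**3. What a straight line does to a curve that is not straight.** Assume complete data and a model with group, linear time and group-by-time terms. Under equal correlation between visits, the fitted group difference is then the ordinary least-squares line through the true differences: slope = Σ(t − t̄)(d − d̄) / Σ(t − t̄)².

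Assumed group differences in HbA1c points: -0.8, -1.0, -0.6, -0.2 at 3, 6, 9, 12 months, and 0 at baseline. These values are illustrative and do not come from the protocol.

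*Follow-up visits only.* t̄ = 7.5 and d̄ = -0.65. The numerator is 0.675 + 0.525 + 0.075 + 2.025 = 3.30 and the denominator is 45. The slope is +0.073 per month.

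*Baseline included as an outcome.* t̄ = 6 and d̄ = -0.52. The numerator is -3.12 + 0.84 + 0 - 0.24 + 1.92 = -0.60 and the denominator is 90. The slope is -0.0067 per month.

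| Month | Assumed | Line, follow-up visits | Line, baseline included |
|---|---|---|---|
| 0 | 0 | – | -0.48 |
| 3 | -0.8 | -0.98 | -0.50 |
| 6 | -1.0 | -0.76 | -0.52 |
| 9 | -0.6 | -0.54 | -0.54 |
| 12 | -0.2 | -0.32 | -0.56 |

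With follow-up visits only, the 6-month effect is understated by 24%, the 12-month effect is 1.6 times its assumed value, and the waning remains visible. With baseline included, the 6-month effect is understated by 48%, the 12-month effect is 2.8 times its assumed value, and the slope is nearly flat. The plan does not say which version would be fitted.

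**4. Other shapes.**
- Plateau without waning (0, 0.8, 1.2, 1.2, 1.2 SD at 0 to 12 months): the follow-up line gives 1.04 SD at 6 months and 1.28 at 12; the five-visit line gives 0.88 and 1.44. A stable effect looks like a growing one. With first-order autoregressive correlation of 0.5 per 3 months, the five-visit figures become 0.80 and 1.38.
- Linear growth: no bias.
- Only the 12- and 24-week visits: the line passes through both points, so nothing is distorted at those visits. Extending the waning case to 12 months would give -1.0 + 6 × (-0.2/3) = -1.4, against an assumed -0.2.

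**5. Categorical visit.** With visit as a factor and treatment-by-visit terms, the expected estimate with complete data equals the true difference at each visit, whatever the curve.

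**The case against.** The strongest reply is that the primary times are already covered. The 6-month test and the one-way ANOVA at 6 and 12 months assume no time shape, and the summary statistics show all four follow-up visits. That stands. It confines the fault to the supporting longitudinal analyses.

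The 12- and 24-week list might also be deliberate: III.C says the primary endpoint is assessed at 6 months and calls the 9- and 12-month visits safety follow-up. But III.A, III.B and III.G all name 12 months for glycaemic control, and the samples are scheduled, so the list conflicts with the plan's own outcome.

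The continuous-time model is only one to be considered, and continuous time does not exclude curvature. That also stands: the misstatement depends on a linear term and on visits beyond 6 months being included.

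A reader might go further and infer three things that the documents do not support.

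- That the protocol describes an HbA1c effect that rises and then falls. It does not. Regeneration is mentioned without timing or glycaemic consequence, III.C ends counselling in both groups (so this alone does not shrink the difference between them), and section II looks to possible long-term benefit.
- That the ANOVA flattens the effect. It omits visits; it distorts none.
- That the conclusion on durability would be reversed. The planned 12-month comparison would still be there to read. The near-zero slope arises only if baseline enters as an outcome, whereas III.G speaks of changes and follow-up visits, which favours the version where waning stays visible.

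**Conclusion.** The point holds in a limited form. The omission of 9 and 12 months from the repeated measures ANOVA is a plain inconsistency with the stated primary outcome and needs no assumption. As a result, the plan has no longitudinal model that estimates the 12-month difference without imposing a time shape. Such a model would also use partial data from the 20% expected to drop out.

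The weakness of the continuous-time model is conditional. With a linear term and visits beyond 6 months, the waning example moves the 6-month effect from -1.0 to between -0.76 and -0.52, and the 12-month effect from -0.2 to between -0.32 and -0.56. These sizes rest on an assumed curve, complete data and equal correlation between visits. They show that the choice matters; they do not predict the trial's bias.

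The primary 6-month comparison, the 12-month one-way ANOVA and the power statement are not affected. The change is worth making, but it does not put the main result at risk.

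**What to change.** In III.G, replace the 12- and 24-week repeated measures ANOVA for HbA1c with one repeated-measures model using the values at 3, 6, 9 and 12 months. Enter visit as a categorical factor with a treatment-by-visit term, and report the 6- and 12-month group contrasts from it. State how baseline HbA1c is handled. Keep any continuous-time model as exploratory only, and state its time terms, its visits and whether it has a group-by-time term.

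The cost is wording, since every HbA1c sample is already scheduled. The model has a few more parameters than a single slope. An unstructured covariance over four visits has 4 × 5 / 2 = 10 parameters, which is a lot for about 24 evaluable patients (2 × 12), so a more parsimonious structure may be needed and should be named in advance.
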